4.7 PHARMACOKINETIC AND PHARMACODYNAMIC ANALYSES

No pharmacokinetic or pharmacodynamics analyses are planned for this study.

4.8 SAFETY ANALYSES

Safety analyses will be performed using the Safety population, with patients grouped according to the treatment actually received. Hypothesis testing will not be performed for any safety analysis.

4.8.1 Exposure of Study Medication

A summary of exposure to study drug, including any reasons not administered (if applicable), dose administered, and total volume administered, will be produced for the safety population.

4.8.2 Adverse Events

All verbatim adverse event terms will be coded using the latest version of MedDRA available at the time of reporting. Adverse event severity will be graded according to National Cancer Institute Common Terminology Criteria for Adverse Events (NCI CTCAE, v5.0).

A treatment-emergent adverse event (TEAE) is defined as any new adverse event reported or any worsening of an existing condition on or after study drug administration. Adverse events with missing onset date will be considered to be treatment emergent. Adverse events with partially missing onset date will also be considered as treatment emergent when the partial date is identified to be on or later than the treatment administration date. An AE will also be considered treatment emergent if the event occurred before the start of treatment and the end date of the AE is either missing or on or after the start of treatment and AE increased in severity or either the initial or most extreme severity grade is missing. TEAEs will be tabulated by preferred terms (PT) within each system organ class (SOC) and will be presented in descending frequency.

Summaries will be provided for each of the following categories:

- All AEs
- Non-serious AEs reported in at least 5% of patient in a treatment group
- All AEs by NCI CTCAE severity

- Serious adverse events (SAEs)
- AEs related to study treatment as assessed by the investigator
- AEs leading to study discontinuation
- AEs resulting in death
- Adverse events of special interest (AESIs) as defined in the protocol (see Section 4.8.2.2)

Listings of AEs, SAEs, AESIs will also be provided.

4.8.2.1 Symptomatic Intracranial Hemorrhage

Intracranial hemorrhage events (ICH) are identified by neuroimaging and are recorded as AEs. Preferred terms for ICH will be based on the latest version of the MedDRA Standardized Medical Query (SMQ) “haemorrhagic central nervous system vascular conditions” (narrow).

For this study, Symptomatic ICH (sICH) is defined as ≥4 points of clinical worsening on the NIHSS compared with the most proximal NIHSS reported, attributed to a bleed on CT scan (preferred) or MRI performed within 36 hours after study drug administration.

To ensure accurate ICH and sICH reporting, central reader data will be compared with the case report forms (CRFs). Sites will be queried if there is a bleeding identified by the central reader without a matching ICH entry in the AE CRF. Counts of ICH and sICH events will be based on the AE reporting. The percentage of patients with sICH within 36 hours will be presented by treatment group and the ICH (symptomatic and asymptomatic) adverse events will be listed. Central reader’s evaluation of ICH, including subtypes, will be presented by treatment group.

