5.2.1 Adverse Events

According to the International Council on Harmonisation guideline for Good Clinical Practice, an adverse event is any untoward medical occurrence in a clinical investigation subject administered a pharmaceutical product, regardless of causal attribution. An adverse event can therefore be any of the following:

- Any unfavorable and unintended sign (including an abnormal laboratory finding), symptom, or disease temporally associated with the use of a medicinal product, whether or not considered related to the medicinal product
- Any new disease or exacerbation of an existing disease (a worsening in the character, frequency, or severity of a known condition) (see Section 5.3.5.9 and Section 5.3.5.10 for more information)
- Recurrence of an intermittent medical condition (e.g., headache) not present at baseline
- Any deterioration in a laboratory value or other clinical test (e.g., ECG, X-ray) that is associated with symptoms or leads to a change in study treatment or concomitant treatment or discontinuation from study drug
- Adverse events that are related to a protocol-mandated intervention, including those that occur prior to assignment of study treatment (e.g., screening invasive procedures such as biopsies or venipuncture)
- Any bleeding that does not qualify as an adverse event of special interest (see Section 5.2.3), including hemorrhagic infarction 1 and 2 (HI1 and HI2), subarachnoid hemorrhage (SAH), and intraventricular hemorrhage (IVH).

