5.2.3 Adverse Events of Special Interest (Immediately Reportable to the Sponsor)

Non-serious adverse events of special interest are required to be reported by the investigator to the Sponsor immediately (i.e., no more than 24 hours after learning of the event; see Section 5.4.2 for reporting instructions). Non-serious adverse events of special interest for this study are as follows:

- Any *sICH* (*defined as ≥4 points of clinical worsening on the NIHSS compared with the most proximal NIHSS reported, attributed to a bleed on CT scan [preferred] or MRI performed within 36 hours after study drug administration*) if not already reported as an SAE. (All other hemorrhages, including HI1, HI2, SAH, and IVH should be reported as an AE.)
- The non-drug specific AESIs:
- Cases of potential drug-induced liver injury that include an elevated ALT or AST in combination with either an elevated bilirubin or clinical jaundice, as defined by Hy's Law (see Section 5.3.5.7)
- Suspected transmission of an infectious agent by the study drug, as defined below
 - Any organism, virus, or infectious particle (e.g., prion protein transmitting transmissible spongiform encephalopathy), pathogenic or non-pathogenic, is considered an infectious agent. A transmission of an infectious agent may be suspected from clinical symptoms or laboratory findings that indicate an infection in a patient exposed to a medicinal product. This term applies only when a contamination of the study drug is suspected.

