4.6.2.5 National Institutes of Health Stroke Scale

National Institutes of Health Stroke Scale is a questionnaire tool used to quantify the impairment caused by stroke. Scores are calculated by summing the responses on the survey, with higher values indicative of a more severe stroke. Missing responses will not be imputed and will result in a missing total NIHSS score. The range for the score is 0 to 42.

For this study, the NIHSS will be conducted at baseline, 24 hours, 72-96 hours, discharge or Day 5, 30 days, and 90 days. It will also be collected at the time of unscheduled imaging to support determination of sICH. All NIHSS scores will be allocated to analysis windows, and a single value per window will be selected for analysis according to the rules in Section 4.6. NIHSS score at Day 90 is a secondary endpoint.

NIHSS scores at each planned post-baseline time point will be summarized descriptively (mean, median, etc.). The van Elteren's test will be used to compare the distribution of tenecteplase and placebo arms, adjusting as specified in Section 4.6. The median treatment differences will be presented with 95% CI based on the Hodges-Lehmann approach for the location shift (median treatment difference).

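### sICH is counted from AE reporting, and the only stated query would not catch a qualifying bleed entered as a non-symptomatic ICH

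*SAP*

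**What the plan says.** SAP 4.8.2.1 defines sICH as at least 4 "points of clinical worsening on the NIHSS compared with the most proximal NIHSS reported, attributed to a bleed on CT scan" (or MRI) within 36 hours of study drug. Protocol 5.2.3 and the footnotes to the endpoint tables give the same definition. It does not restrict the type of bleed.

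On counting, SAP 4.8.2.1 states: "Counts of ICH and sICH events will be based on the AE reporting". On checking, it states an aim, "To ensure accurate ICH and sICH reporting, central reader data will be compared with the case report forms (CRFs)", and then one action: "Sites will be queried if there is a bleeding identified by the central reader without a matching ICH entry in the AE CRF". The central reader's own "evaluation of ICH, including subtypes, will be presented by treatment group". The SAP does not say that this reading enters the sICH count.

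Protocol 5.2.3 gives the definition and then adds: "All other hemorrhages, including HI1, HI2, SAH, and IVH should be reported as an AE". Protocol 5.2.1 lists the same four types after the words "Any bleeding that does not qualify as an adverse event of special interest".

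An NIHSS is required for any ICH within 36 hours of study drug (Protocol Appendix 1 footnote h and Appendix 7; SAP Appendix 2 footnote h). SAP 4.6.2.5 says of the NIHSS: "It will also be collected at the time of unscheduled imaging to support determination of sICH".

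**The concern.** The definition turns on symptoms, while the protocol's list of examples is sorted by radiological type. Suppose a patient has an SAH or HI2 at 20 hours with a 6-point NIHSS rise attributed to the bleed. The definition makes this sICH. A site that reads the list as a sorting rule by bleed type would enter an ordinary ICH adverse event. The count then follows that entry, and the stated query has nothing to react to because an ICH entry exists.

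sICH within 36 hours is the first safety endpoint listed in SAP 2.2.5 and the only count in the Table 4 monitoring boundary. An undercount would lower the reported rate and make the boundary less sensitive. It could also vary between sites according to which sentence each one follows.

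**Working it through.** **1. Does the stated check reach the error?** Take bleeds that truly meet the sICH definition and follow each possible entry:

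- No ICH entry on the AE form: the central reader sees the bleed, no entry matches, and the site is queried. The error is caught.
- Entered as sICH: counted correctly.
- Entered as an ICH that is not symptomatic: an entry matches, so the stated query is not raised. The event stays out of the sICH count.

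The third route is open. Protocol 7.1 and SAP 3.2 describe the central reader's task as reading images, and neither says that the reader sees the change in NIHSS. No section of either document sets the recorded NIHSS change against an ICH entry, although both are collected.

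**2. The plan's own figure.** SAP 4.10 states a crossing probability of at most 0.05 at a true sICH rate of 10%, with boundaries 8/25, 12/50, 19/100, 32/200 and 36/228. The check is an exact sequential binomial calculation: at each look, add the probability that the cumulative count reaches the boundary for the first time. At 10% the five looks give

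0.00226 + 0.00256 + 0.00351 + 0.00391 + 0.00113 = 0.0134.

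The stated bound is met.

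**3. Illustration of an undercount.** Let m be the share of true sICH entered as non-symptomatic, with each event missed independently. Then

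counted rate = true rate × (1 − m).

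Neither m nor any true rate above 10% comes from the documents; both are assumptions. At a true 15%, the counted rate is 0.15 × 0.9 = 13.5%, 0.15 × 0.8 = 12.0% and 0.15 × 0.7 = 10.5% for m = 10%, 20% and 30%.

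Probability of crossing Table 4 at any of the five looks:

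| True rate | m = 0 | m = 10% | m = 20% | m = 30% |
|---|---|---|---|---|
| 10% | 0.013 | 0.004 | 0.001 | <0.001 |
| 15% | 0.467 | 0.241 | 0.089 | 0.023 |
| 20% | 0.966 | 0.862 | 0.625 | 0.311 |

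As a check on one cell, a counted rate of 12% gives 0.00702 + 0.01055 + 0.02093 + 0.03854 + 0.01190 = 0.0889.

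Under-labelling therefore matters to the boundary only if the true rate is well above 10%. At 10% or below, crossing is unlikely with or without it.

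**The case against.** A reader might infer that the protocol tells sites to treat every HI1, HI2, SAH or IVH as an ordinary adverse event. It does not. In 5.2.3 the list follows the sICH definition and begins with the word for hemorrhages other than that event; in 5.2.1 it is limited to bleeding that fails to qualify. Read strictly, a listed type with attributed worsening of at least 4 points is still sICH. The protocol's summary of changes also says the special-interest list was aligned with the definition. This objection stands: the wording is ambiguous and excludes nothing. But neither section says outright that a listed type can be sICH.

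A reader might also infer that 24-hour reporting is lost. Mostly it is not. The special-interest category covers events not already reported as serious, and a bleed with that much neurological worsening would usually meet a seriousness criterion in Protocol 5.2.2, which carries the same 24-hour duty.

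Other safeguards exist. All ICH events are listed, central subtypes are tabulated by arm, the iDMC sees unblinded adverse event data, and the boundary is non-binding. Site staff are blinded, so a bias between arms is not shown. These safeguards keep the bleed visible, but they do not correct the sICH count.

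The aim stated in SAP 4.8.2.1 includes sICH accuracy, and a review charter outside these documents may add checks. The documents also do not describe an sICH tick-box on the AE form. The point therefore concerns the check as written. Finally, the tenecteplase rates of symptomatic hemorrhage cited in Protocol 1.2.2 run from 0% to 8% under varying definitions, so the 15% and 20% rows above are stress cases and not expectations.

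**Conclusion.** The point holds in a limited form. As written, the SAP's only query does not test symptom status, so a qualifying bleed entered as a non-symptomatic ICH would stay out of the endpoint and the Table 4 count. The protocol's list of examples makes that entry more likely without requiring it.

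The documents give no mix of bleed types and no mislabelling rate, so they do not support any claim about the actual size of an undercount or about its direction between arms. The fall from 0.47 to 0.24, 0.09 or 0.02 depends on an assumed true rate of 15% and assumed missed shares of 10%, 20% and 30%. Severity is minor: this is a cheap improvement to a check that already exists.

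**What to change.** In SAP 4.8.2.1, add a programmed check run without treatment codes. It should flag any ICH of any type (AE entry or central read) on a scan within 36 hours of study drug, with NIHSS worsening of at least 4 points from the most proximal earlier NIHSS, that is not reported as sICH. It should also flag the reverse: an event reported as sICH without such a bleed or such worsening. Query the site on attribution for each flagged case, before each iDMC look and before database lock. Use the reconciled count for the endpoint and for Table 4.

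The check should only raise a query. It should not redefine the endpoint: the definition requires the worsening to be attributed to the bleed, and a rule based on bleed plus NIHSS change alone would also take in incidental bleeds in patients who worsened for another reason.

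In Protocol 5.2.1 and 5.2.3, state that a bleed of any type, including HI1, HI2, SAH and IVH, is sICH if it meets the definition, and that the list covers only those that do not. The SAP check works by itself if the protocol is not amended.

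The cost is one programmed listing, a few extra site queries and two clarifying sentences. No new assessments, scans or readers are needed.

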4.8.2.2 Adverse Events of Special Interest

AESIs for this study include the following non-serious AEs:

- sICH events.
- The non-drug specific AESIs:
 - Cases of potential drug-induced liver injury that include an elevated alanine aminotransferase (ALT) or aspartate aminotransferase (AST) in combination with either an elevated bilirubin or clinical jaundice, as defined by Hy's Law. This includes
 - Treatment-emergent ALT or AST >3 × upper limit of normal (ULN) in combination with total bilirubin >2 × ULN
 - Treatment-emergent ALT or AST >3 × ULN in combination with clinical jaundice
 - Suspected transmission of an infectious agent by the study drug, as defined below:
 - Any organism, virus, or infectious particle (e.g., prion protein transmitting transmissible spongiform encephalopathy), pathogenic or non-pathogenic,

is considered an *infectious agent*. A transmission of an infectious agent may be suspected from clinical symptoms or laboratory findings that indicate an infection in a patient exposed to a medicinal product. This term applies only when a contamination of the study drug is suspected.

AESIs will be summarized by treatment group using the safety population and listed.

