5.1.1.1 Bleeding

The most common complication encountered during tenecteplase therapy is bleeding. This may be either superficial from punctures or damaged blood vessels or internal bleeding at any site or body cavity. Bleeding may result in life-threatening situations, permanent disability, or death.

- The incidence of ICH, especially sICH, in patients with AIS is higher in alteplase-treated patients than placebo-treated patients in published studies (for detailed information, see the alteplase USPI).

The type of bleeding associated with thrombolytic therapy can be divided into two broad categories:

- Internal bleeding, involving intracranial and retroperitoneal sites, or the gastrointestinal, genitourinary, or respiratory tracts
- Superficial or surface bleeding, observed mainly at vascular puncture and access sites (e.g., venous cutdowns, arterial punctures) or sites of recent surgical intervention

Management of Bleeding

Patients will be excluded for the presence of conditions related to risks of bleeding (as outlined in Section 4.1.2, Exclusion Criteria).

Fibrin, which is part of the hemostatic plug formed at needle puncture sites, may be lysed during tenecteplase therapy. In the event of serious bleeding (not controlled by local pressure) in a critical location (intracranial, gastrointestinal, retroperitoneal, or

pericardial), study drug should be discontinued immediately, and any concomitant heparin or antiplatelet agents should be discontinued immediately and appropriate treatment initiated.

Guidelines for management of patients who develop bleeding are provided in [Table 4](#).

In addition, any *sICH* events, if not already reported as an SAE by the investigator, are considered non-serious adverse events of special interest for this study (Section [5.2.3](#)) and should be reported and submitted to the Sponsor (Section [5.4.2](#)).

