5.3.5.7 Abnormal Liver Function Tests

The finding of an elevated ALT or AST ($>3 \times \text{ULN}$) in combination with either an elevated total bilirubin ($>2 \times \text{ULN}$) or clinical jaundice in the absence of cholestasis or other causes of hyperbilirubinemia is considered to be an indicator of severe liver injury (as defined by Hy's Law). Therefore, investigators must report as an adverse event the occurrence of either of the following:

- Treatment-emergent ALT or AST $>3 \times \text{ULN}$ in combination with total bilirubin $>2 \times \text{ULN}$

- Treatment-emergent ALT or AST $>3\times$ ULN in combination with clinical jaundice

The most appropriate diagnosis or (if a diagnosis cannot be established) the abnormal laboratory values should be recorded on the Adverse Event eCRF (see Section 5.3.5.2) and reported to the Sponsor immediately (i.e., no more than 24 hours after learning of the event), either as a serious adverse event or an adverse event of special interest (see Section 5.4.2).

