6.6 INTERIM ANALYSES

6.6.1 Planned Interim Analyses

Two safety only interim analyses are planned when the first 25 and 50 patients have completed the *72–96 hours visit* assessment post-randomization, respectively. One efficacy interim analysis is planned when 50% (i.e., 228) of the total patients have

completed the 90-day assessment to monitor both the efficacy and safety of tenecteplase vs. placebo. The safety data to be summarized in the safety interims include deaths, SAEs, non-serious AEs, treatment-related AEs, and AEs of special interest. The study may be halted if *an* excessive number of sICH events are observed, and the details of the suggested stopping boundaries for interim safety evaluations will be provided in the study *SAP*. At the efficacy interim analysis, where the primary efficacy analysis will be performed on 50% of patients, a type I error of 0.003 will be allocated for the interim efficacy evaluation based on the Lan-DeMets theory for α -spending function that approximates the O'Brien-Fleming boundary (DeMets and Lan 1994). Additional criteria for recommending that the study be stopped for positive efficacy may be added to the iDMC charter. If the study continues beyond the efficacy interim analysis, the critical value at the final primary efficacy analysis would be adjusted accordingly to maintain the protocol-specified overall type I error rate, i.e., the final efficacy analysis will be performed at the 0.049 significance level to maintain an overall family-wise type 1 error rate of 0.05.

Details of the statistical methodology for the efficacy interim analyses will be documented in the *study SAP*. The iDMC charter will document potential recommendations the iDMC can make as a result of the analyses (e.g., stop the study for positive efficacy, stop the study for safety concerns). During the interim analyses, the Sponsor will remain blinded to individual treatment assignment. The interim analyses will be conducted by an independent statistical entity and reviewed by the iDMC. Interactions between the iDMC and Sponsor will be carried out as specified in the iDMC charter to ensure integrity of study conduct.

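### The SAP's AESI summary is limited to non-serious events, so it leaves out the gravest cases and would understate sICH beside the SAP's own sICH summary

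*SAP*

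**What the plan says.** SAP 4.8.2.2 introduces its list with "AESIs for this study include the following non-serious AEs". The list has three items: sICH, potential drug-induced liver injury meeting Hy's Law, and suspected transmission of an infectious agent by the study drug. The section ends: "AESIs will be summarized by treatment group using the safety population and listed". SAP 4.8.2 sends the reader to the same place, naming among its planned summaries "Adverse events of special interest (AESIs) as defined in the protocol (see Section 4.8.2.2").

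The restriction originates in the protocol. Section 5.2.3, which sets the 24-hour reporting duty, says "Non-serious adverse events of special interest for this study are as follows" and counts an sICH only "if not already reported as an SAE". Section 5.1.1.1 repeats the rule for sICH: such events, "if not already reported as an SAE by the investigator, are considered non-serious adverse events of special interest for this study". Section 5.3.5.7 has Hy's Law cases reported "either as a serious adverse event or an adverse event of special interest", so the two routes are alternatives.

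The protocol's analysis section (6.5) plans by-arm summaries of treatment-emergent events, including hemorrhage and other AESIs, and states no seriousness limit. For the safety interims, Protocol 6.6.1 lists "deaths, SAEs, non-serious AEs, treatment-related AEs, and AEs of special interest".

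**The concern.** A category that tells sites how to report an event has become the filter for an analysis table. That filter selects on severity of consequence: the worse the event, the more surely it is excluded. A reader who opens a table of adverse events of special interest in a thrombolysis trial expects to find the important bleeds there. As written, the table would hold only those the investigator judged non-serious.

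Two things are at stake. For sICH, one report would carry two by-arm counts for the same population, and the one labelled AESI would be the lower. For Hy's Law and suspected-transmission events, the AESI table is the only output that groups cases under the protocol's definition, so serious cases would have no grouped summary.

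**Working it through.** No figure in the plan needs reproducing. The check compares definitions and outputs, followed by one hand illustration.

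**Which events are excluded.** Under Protocol 5.2.2, an event that is fatal, is life-threatening, prolongs hospitalization, or causes significant disability is an SAE. Table 5 in Protocol 5.3.3 also requires Grade 4 and 5 events to be reported as SAEs. Under SAP 4.8.2.2 an SAE is not an AESI. So every fatal or life-threatening case of all three types falls outside the AESI summary and listing. This step needs no assumed rate.

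For the remaining sICH cases, the definition requires at least 4 points of NIHSS worsening attributed to a bleed. In a hospitalized stroke patient that would often meet a seriousness criterion. This is an inference; no document quantifies it.

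**Where each excluded case can still be found.**

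- Serious sICH: SAP 4.8.2.1 gives the percentage of patients with sICH within 36 hours by arm, from AE reporting and with no seriousness limit. It also lists all ICH events and presents the central reader's evaluation. The SAE summary and listing (SAP 4.8.2) include these cases, and the boundary in SAP 4.10, Table 4, counts patients with sICH.
- Serious Hy's Law or suspected-transmission cases: only the general AE and SAE outputs of SAP 4.8.2, by preferred term. Laboratory summaries do not help, because SAP 4.8.3 covers baseline values only.

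**Illustration for sICH.** Inputs: n = 228 per arm (SAP 2.3, taken as all dosed), and rates of 1% and 6.5%, both reported for earlier tenecteplase studies in Protocol 1.2.2. Those studies had other populations, and the sICH definitions they cite are not this trial's, so the rates only set a range. The serious share s is an assumption.

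Cases in SAP 4.8.2.1 = n × rate: 228 × 0.065 = 14.8, and 228 × 0.01 = 2.3.

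Cases in the AESI row = n × rate × (1 − s):

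| Serious share s | 6.5% rate (14.8 cases) | 1% rate (2.3 cases) |
|---|---|---|
| 50% | 7.4 | 1.1 |
| 80% | 3.0 | 0.5 |
| 95% | 0.7 | 0.1 |
| 100% | 0 | 0 |

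The SAP 4.8.2.1 figure stays at 14.8 or 2.3 in every row. With AESIs defined regardless of seriousness, the two outputs would draw on the same sICH cases.

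**The case against.** A reader might infer that nearly all sICH disappears from the report, or that the iDMC would not see the bleeding rate. The documents do not support either inference. The output meant to show sICH is SAP 4.8.2.1, which has no seriousness filter. sICH is a named safety endpoint (SAP 2.2.5), and sites are queried when the central reader sees a bleed with no matching AE entry. The interim package includes SAEs as well as AESIs, and the stopping boundary counts sICH patients directly. No stopping rule uses the AESI row. The words nearly all would also need a serious share that the plan does not give.

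It can also be said that the SAP is only following the protocol's definition, that a labelled non-serious subset does not contradict the full count, and that no hypothesis test is run on safety data (SAP 4.8). These points hold, and they limit the consequence to presentation. They do not remove it: Protocol 6.5 states no seriousness limit for the AESI summary, and the SAP gives no reason for the narrower set. The verb include in SAP 4.8.2.2 leaves slight room for a wider reading, but Protocol 5.2.3 and 5.1.1.1 point to the restrictive one.

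On the other two event types, the gap is real but thin. Such events are presumably rare, and the plan gives no expected number. The chemistry panel is scheduled only at screening (Protocol Appendix 1) and is described as electrolytes (Protocol 4.5.10), so no scheduled post-baseline liver tests would feed a Hy's Law table. Serious cases stay in the general tables and under 24-hour reporting.

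**Conclusion.** The point holds as a flaw in one by-arm safety table and its listing. As worded, the AESI set omits every serious case, and therefore all fatal and life-threatening ones, although Protocol 6.5 plans the summary without that limit. This part rests on the text alone.

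For sICH the effect is a misleadingly low row beside a correct figure elsewhere. Its size depends on an unstated serious share: in the illustration, 7.4 to 14.8 of 14.8 cases per arm would be missing at the 6.5% rate, and 1.1 to 2.3 of 2.3 at the 1% rate, for shares of 50% to 100%. For Hy's Law and suspected transmission, serious cases would have no grouped summary, though few would be expected. No efficacy result, safety endpoint or stopping boundary changes. The correction is worth making because it is cheap and the omitted cases are the gravest.

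**What to change.** In SAP 4.8.2.2, define AESIs for analysis as all sICH, Hy's Law and suspected-transmission events regardless of seriousness, shown with serious and non-serious sub-rows. Make matching changes in SAP 4.8.2, where the AESI summary is tied to the protocol definition, and in the interim table shells. Keep the non-serious wording only as the reporting rule of Protocol 5.2.3, which does not change.

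The cost is a sentence of definition, the matching wording and one table filter. There are two small drawbacks. The same event will appear in both the SAE and AESI tables, which is harmless because the categories in SAP 4.8.2 already overlap. The SAP must also say openly that its analysis definition is broader than the protocol's reporting category.
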